2.3 Summary

Known and potential risks: HD patients differ from healthy volunteers in a number of ways. Weight loss, insomnia, depression, concomitant drug treatments, comorbid affective disorders, and reduced cognitive reserve are among the major differences to be expected in HD Subjects that can influence tolerability.

There is a weight loss in early stage HD (reference accessed at <http://www.ncbi.nlm.nih.gov/pubmed/12427878>). In men, mean BMI (\pm SE) was 25.90 ± 0.34 kg/m² among case Subjects and 27.68 ± 0.16 kg/m² among control Subjects ($p < 0.0001$). Corresponding values for women were 24.34 ± 0.43 kg/m² for case Subjects and 26.63 ± 0.21 kg/m² for control Subjects ($p < 0.0001$). In addition, when case Subjects with HD were restricted to those with disease duration of <1 year and absence of both chorea and dystonia, case Subjects still had lower BMI than control Subjects in both genders. Assuming that Subjects in the HD and control groups were approximately the same height, this suggests that the HD patients are 6-

8% lighter than controls. We do not feel that this small difference will necessitate a dose adjustment.

The NOAEls of SRX246 in rat and dog are 75 mg/kg/day and 30 mg/kg/day, respectively. The human equivalent numbers are 12.1 and 16.7 mg/kg/day or 1077 and 1463 mg/day in an 89 kg man. Since we propose to give Subjects a maximum of 320 mg of SRX246 per day (about one-third the lower NOAEL), the compound should be safe to use. We have not given normal volunteers 160 mg BID but we have given them 320 mg once a day safely in our SAD Phase I study. The 120 mg bid dose was safe and well tolerated in the MAD study. In the present trial, we escalate from 80 mg BID to 160 BID, with each escalation Subject to review of safety data. As shown above, we have modeled the 160 mg BID dose and estimates provide a good safety margin

Dose limiting toxicity was not observed in the single ascending dose (SAD) trial, multiple ascending dose (MAD) trial, or the Experimental Medicine (human fMRI) study. SRX246 was safe and well tolerated at the highest doses studied--320 mg in the SAD and 120 mg BID x 14 days in the MAD studies. The adverse event profile of SRX246 in humans is not fully known, and adverse reactions may occur following treatment with SRX246. All Subjects participating in clinical trials will be observed closely for adverse reactions potentially related to study drug administration.

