An additional consideration is that using the asymptotic test with our estimated sample size might not be optimal. The asymptotic test can be inaccurate with smaller sample sizes, especially when π_P (or π_T) is close to 1, as is anticipated in the proposed study (cf Table 4) (Fagerland 2011). Computer-intensive exact methods can have better performance under these conditions (Santner 2007). The exact method discussed by Wang (2010) will be used for the proposed analysis of tolerability and safety (the latter is discussed below). Wang's method appears to have superior performance to other approaches, and software is readily available (Wang 2013).

Secondary Aim: Safety. The secondary aim of the analysis is safety, with the endpoint defined as the proportion of participants who experience an adverse event (AE). A non-inferiority analysis for safety will be performed, similar to that discussed for tolerability. Primary focus will be on the comparison of 160mg vs placebo. H_0 for non-inferiority will be evaluated using the methods previously described with the same margin of difference, $\delta = 0.50$.

Consistent with the recent JAMA Guide to Statistics and Medicine (Detry 2014) the analysis will be performed consistent with the intent-to-treat principle, meaning an attempt will be made to analyze all enrolled patients. Missing data methods, such as imputation, might be used to handle dropout (note this is not an issue for the tolerability analysis as the proportion of completers is the endpoint).

Exploratory Aim: Activity of Measures. The exploratory aim is to examine several measures of irritability and other problem behaviors and clinical assessment for activity signal. Measures will be compared to each other and also compared to clinical assessments in order to examine relative

effect sizes. The endpoint will be rate of change (slope) over 12 weeks. Linear mixed models (LMMs) (Verbeke 2000) will be used to examine slope differences among the placebo and treatment groups. LMMs are appropriate for the analysis because they account for dependency due to repeated measures and can be estimated with maximum likelihood (ML) procedures.

Consistent with the intent-to-treat principle, ML estimation can accommodate missing data under the assumption that the missing data mechanism is ignorable (Little 1987).

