1. STUDY DESIGN

This is a 3-arm, multicenter, randomized, placebo-controlled, double-blind, 12-week, dose escalation study of SRX246 in irritable study participants with early symptomatic HD. We initially planned to randomize $N = 108$ participants to the study arms (36 per arm), with one arm being placebo and the other arms being different final doses of SRX246. The treatment for each study participant was assigned by a randomized code.

Following an initial screening visit, study participants fulfilling the study inclusion and exclusion criteria entered a pre-treatment screening phase, of no longer than 30 days, to permit evaluations to confirm eligibility for inclusion into the study. At the completion of the screening period, eligible participants were randomized at the baseline visit to receive either placebo or final doses of SRX246 of 120 mg twice daily or 160 mg twice daily during the double-blind treatment phase. At baseline, study participants in the active groups were to receive 80 mg twice daily for 2 weeks, then escalate to 120 mg twice daily for 4 weeks. Thereafter, one group of active study participants were to continue to take 120 mg of SRX246 twice daily for an additional 6 weeks, and the second group of participants was to increase their dose to 160 mg of SRX246 twice daily for 6 weeks. Total dosing duration was 12 weeks. Study participants in the placebo group were to receive the same number of capsules that are identical in appearance to the capsules that contain SRX246 during the trial, to preserve the blind. In all groups, step-up dose escalation occurred if patients did not experience dose-limiting adverse events. Patients who could not tolerate their final dose of drug (or placebo) could have their dose reduced without compromising the blinding.

Study participants had periodic scheduled visits either "in-person" or by "telephone". An electronic (smart phone or table) diary known as the eDiary prompted participants to take their capsules twice a day and asked whether they did so. The study participants and their study partners were asked to answer daily questions having to do with irritability and behavior (also recorded in the eDiary). Visits (with varying windows) were to occur at week 0 (baseline), 2, 4, 6, 8, 10, and 12. Data from all study participants who were given placebo will be combined, and two pairwise tests will be performed (120 mg vs placebo, 160 mg vs placebo).

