3. SECONDARY ENDPOINT

The secondary endpoint for safety is defined as the proportion of study participants who experience any treatment-emergent (starting at or after the first dose of study medication) adverse event (AE) or serious adverse event (SAE). For the purposes of this study, a treatment emergent adverse event (AE) is any untoward medical occurrence associated with the use of a drug in humans, whether or not considered drug related. FDA, Office of Human Research Protection (OHRP) and NeuroNEXT CIRB requirements for reporting AEs will be followed. AEs are generally detected in two ways:

- Clinical → Symptoms reported by the study participant or signs detected on examination
- Ancillary Tests → Abnormalities of vital signs, laboratory tests, and other diagnostic procedures

If discernible at the time of completing the AE source documentation, a specific disease or syndrome rather than individual associated signs and symptoms should be identified by the Site Investigator and recorded in the AE documentation. However, if an observed or reported sign, symptom, or clinically significant laboratory anomaly is not considered by the Site Investigator to be a component of a specific disease or syndrome, then it should be recorded as a separate AE in the source documentation. Clinically significant laboratory abnormalities, such as those that require intervention, are identified as such by the Site Investigator.

Each clinical study site's Principal Investigator and research team (co-investigators, research nurse, and clinical trial coordinator) are responsible for identifying and reporting AEs through the NeuroNEXT Online Adverse Event Reporting System. The AE definitions and reporting procedures used for this study comply with all applicable U. S. Food and Drug Administration (FDA) regulations and International Conference on Harmonization (ICH) guidelines. The Site Investigator will carefully monitor each study participant throughout the study for possible AEs. All AEs will be documented on CRFs designed specifically for this purpose. It is important to report all AEs, especially those that result in permanent discontinuation of the investigational product, whether serious or non-serious. Local site investigators are also required to fulfill all reporting requirements of their local institutions.

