Study participants who sign consent and receive investigational treatment will be monitored for AEs from the time they sign consent through week 12 or the end of their study participation. This study utilized the CTCAE version 4.03 coding system for AE recording. AEs reported using CTCAE will be recoded into MedDRA terms by the DCC.

At each visit, the participant will be asked "Have you had any problems or symptoms since your last visit?" in order to determine the occurrence of AEs. If the study participant reports an AE, the Investigator will determine:

- Type of event
- Date of onset and resolution (duration)
- Severity (mild, moderate, severe, life-threatening, results in death)
- Seriousness (does the AE meet the definition of an SAE)
- Causality, relation to investigational product and disease
- Action taken regarding investigational product
- Outcome

All clinical AEs are recorded in the AE data entry template in the study participant's study binder. The sites should fill out the AE data entry template and enter the information into the Online Adverse Event Reporting System (AERS) within 5 working days / 7 calendar days of the site learning of a new AE or receiving an update on an existing AE. Entries in the AE data entry template will include the following:

- Name and severity of the AE
- Date of onset
- Date of resolution

- Relationship to study drug
- Action taken
- Primary outcome of event

The severity of all AEs will be graded according to CTCAE, version 4.03. Any AE not listed in the CTCAE will be graded as follows:

- Grade 1 – Mild: Transient or mild discomfort; No limitation in activity; No medical intervention/therapy required
- Grade 2 – Moderate: Mild to moderate limitation in activity; Some assistance may be needed; No or minimal medical intervention/therapy required
- Grade 3 – Severe: Marked limitation in activity, some assistance usually required; Medical intervention/therapy required; Hospitalizations possible
- Grade 4 – Potentially Life-Threatening: Extreme limitation in activity; Significant assistance required; Significant medical intervention/therapy required; Hospitalization or hospice care probable
- Grade 5 – Death: The AE results in death

The Site Investigator is initially responsible for classifying AEs as serious or non-serious. An AE is considered serious if it meets one or more of the following criteria:

- Results in death

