8. SECONDARY ANALYSIS

Secondary Objective: *The secondary objective is to evaluate the safety of SRX246.*

The safety objective will be met by conducting a non-inferiority test of the proportion of study participants with AEs or SAEs among the placebo group and each of the treatment groups (separate tests for placebo vs 120 mg and placebo vs 160 mg). The safety analysis will be conducted in a similar manner as the tolerability analysis. Each study participant will be classified as having experienced a treatment-emergent AE or SAE (event = "Yes") or not (event = "No"). Suppose the proportion of events in the placebo group is now denoted as π_{placebo} and the proportion of events in the 120 mg group is now $\pi_{120\text{mg}}$, with $\theta = \pi_{\text{placebo}} - \pi_{120\text{mg}}$. The same onesided CI will be used to test the same null hypothesis ($H_0: \theta \geq \delta$) with the same threshold ($\delta = 0.5$) as in the tolerability analysis. Each treatment group (120 mg, 160 mg) will be compared to the placebo group using $\alpha = 0.025$, meaning a $1 - \alpha = 0.975$ one-sided CI will be used for each test. Results will be summarized as shown in Table 3 below.

Table 3. Summary of Safety Analyses

	Placebo (N = XX)	120 mg (N = XX)	160 mg (N = XX)
Any AE	XX (XX%)	XX (XX%)	XX (XX%)
Any Treatment-Related AE	XX (XX%)	XX (XX%)	XX (XX%)
Any Serious AE	XX (XX%)	XX (XX%)	XX (XX%)
Early Drug Withdrawals (Any)	XX (XX%)	XX (XX%)	XX (XX%)
Early Drug Withdrawals (Due to AE)	XX (XX%)	XX (XX%)	XX (XX%)
Early Terminations (Any)	XX (XX%)	XX (XX%)	XX (XX%)
Early Terminations (Due to AE)	XX (XX%)	XX (XX%)	XX (XX%)
Deaths (Any)	XX (XX%)	XX (XX%)	XX (XX%)
Deaths (Due to AE)	XX (XX%)	XX (XX%)	XX (XX%)

In addition to an overall comparison, this hypothesis will be repeated for assessing the percentage of study participants having at least one treatment-emergent AE within each MedDRA system organ class (SOC). If there are specific differences within any specific SOC, then additional tests will compare differences across groups for specific MedDRA preferred terms in order to further explore the cause of the observed differences. Finally, the subset of treatment-related SAEs will be analyzed in the same manner described above.

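### The 160 mg safety comparison counts any AE from first dose, and no planned analysis isolates the period on 160 mg; a supplementary table by onset period would supply one

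*SAP*

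**What the plan says.** SAP 3 defines the safety endpoint as "the proportion of study participants who experience any treatment-emergent (starting at or after the first dose of study medication) adverse event" or serious adverse event, and SAP 8 applies it as a single yes/no: "Each study participant will be classified as having experienced a treatment-emergent AE or SAE". Participants are "monitored for AEs from the time they sign consent through week 12 or the end of their study participation". Each dose is tested against placebo. The same comparison is repeated within each system organ class (SOC), with preferred terms to follow if an SOC differs. Neither the tests nor SAP Table 3 are split by dosing period, although SAP 3 has the investigator record each event's onset date.

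On dosing, SAP 1 states that "study participants in the active groups were to receive 80 mg twice daily for 2 weeks", then 120 mg for 4 weeks, after which "the second group of participants was to increase their dose to 160 mg of SRX246 twice daily for 6 weeks". Protocol 2.1.3 and 3 agree, and Protocol 6.5 places the change at the week 6 visit. Protocol 8 instead puts the second increase 2 weeks after the first, which would be week 4.

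For safety, Protocol 8.2 says: "Primary focus will be on the comparison of 160mg vs placebo". Protocol 2.3 says: "We have not given normal volunteers 160 mg BID". The same sentence adds that a 320 mg once-daily dose was given safely in the single-dose study.

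**The concern.** Up to the step, the 160 mg arm is dosed exactly as the 120 mg arm. Anyone in it who reports an AE in that time is already a 'Yes' before taking 160 mg, and a later event on 160 mg cannot change the flag. If harm appears only at 160 mg, the overall contrast with placebo understates it, and the understatement grows with the background AE rate. The same happens within each SOC, to a smaller degree because SOC rates are lower. At stake is what the report can say about the highest dose, which is where the protocol puts its safety focus.

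**Working it through.** **Plan's own figure.** The documents give no sample size, power or AE rate for the safety test. The 36 per arm comes from the completer test. With completer rates 0.80 and 0.60, margin 0.50, one-sided alpha 0.025 and power 80%:

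n = (1.960 + 0.842)² × (0.80×0.20 + 0.60×0.40) / (0.50 − 0.20)² = 7.85 × 0.40 / 0.09 = 34.9, so 35 (power 80.1%), or 81.2% at 36.

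I use 36 per arm below.

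**Dilution.** Let e be the chance of an AE before the step, equal in the arms compared, and let a (placebo) and b (160 mg) be the chances of an AE after it, with the periods independent. The whole-trial rates are 1 − (1−e)(1−a) and 1 − (1−e)(1−b), so

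whole-trial difference = (1 − e)(b − a).

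The late difference is reduced by the fraction e. With a constant hazard, a 12-week placebo rate p and a step at week 6, e = 1 − (1−p)^(6/12).

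**Results.** Assumptions: no drug effect before week 6, hazard doubled after it, everyone observed. Power is for an exact unconditional one-sided 0.025 score test for excess AEs at 36 per arm. The SAP does not plan that test; it serves only as a measure of information.

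| Assumed 12-week placebo AE rate | Dilution e | Whole-trial excess | Late excess | Power, whole trial | Power, late |
|---|---|---|---|---|---|
| 20% | 11% | 0.084 | 0.094 | 13% | 19% |
| 30% | 16% | 0.114 | 0.137 | 16% | 27% |
| 50% | 29% | 0.146 | 0.207 | 22% | 42% |
| 60% | 37% | 0.147 | 0.232 | 26% | 49% |
| 70% | 45% | 0.136 | 0.248 | 27% | 55% |
| 80% | 55% | 0.111 | 0.247 | 25% | 62% |
| 90% | 68% | 0.068 | 0.216 | 18% | 63% |

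Check at 70%: the 6-week placebo rate is 1 − √0.30 = 0.452. Doubling the late hazard gives 1 − 0.30 = 0.70 late and 1 − 0.30^1.5 = 0.836 over the trial. The excesses are 0.248 and 0.136, and 0.136/0.248 = 0.55, a loss of 45%.

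With the late hazard tripled, power at rates of 50–80% is 56–63% (whole trial) against 86–95% (late).

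**Sensitivity of the dilution.**
- Step at week 4, e = 1 − (1−p)^(4/12): 20.6% at a 50% rate and 41.5% at 80%.
- 70% of the hazard falling in weeks 0–6: 38% and 68%.
- Participants differing in AE proneness (gamma frailty, variance 0.5–2, late hazard ratio 1.5–3): 34–47% and 49–60%.
- Within an SOC with a 10% rate: 1 − √0.90 = 5%.
- Drug also raising early AEs (hazard ratio 1.5 early, 2 late): 2% at a 50% rate, 43% at 80%.
- Hazard doubled throughout, 50% rate: whole-trial excess 0.25 against 0.207 late, so the planned count is the larger. Its power is 59–63% against 42–55% at rates of 50–70%. At 80% the late excess is larger again (0.247 against 0.16).

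**The case against.** The strongest reply is that the plan asks a different question. Each randomised regimen is compared with placebo, as randomised, and AEs during titration belong to the regimen's effect. That the active arms are dosed alike at first bears directly only on 160 mg against 120 mg, which is not a planned test. This stands: the endpoint is legitimate and should stay. If the drug acts at all doses, it can also be the more powerful count.

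Three stronger readings are tempting, and the documents do not support them.

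- **That participants with an early AE cannot show harm from 160 mg.** This is true only of the overall flag. The SOC and preferred-term tests, the serious and treatment-related AE rows, withdrawals due to AE and the treatment-related SAE analysis can all register a later event. The primary endpoint in SAP 2 also counts as a non-completer anyone who finishes below the assigned dose. What remains is that none of these is tied to the period on 160 mg.
- **That the contrast is diluted by 30–55%.** That range needs an assumed 12-week AE rate of 50–80% and no drug excess at 80 or 120 mg. Neither is in the documents. Rates of 20–90% give 11–68%.
- **That the endpoint mostly measures the lead-in.** With the late hazard doubled, the share of 160 mg 'Yes' cases arising before week 6 is 0.293/0.646 = 45% at a 50% rate and 0.368/0.747 = 49% at 60%. It passes half only at higher rates.

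It is also fair to say that SAP 8 has a larger fault. It carries over the placebo-minus-active sign and the 0.5 margin from tolerability, so excess AEs on drug favour rejection. That is a separate problem, which an onset-period table does not repair.

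**Conclusion.** The point holds as a gap in the planned reporting, not as an error in the endpoint. An excess confined to the period on 160 mg is understated in the overall any-AE contrast by the chance of an earlier AE. The size is known only conditionally: it assumes no drug excess before the step, a constant hazard, independent periods and an AE rate that the documents do not supply. Within SOCs the loss is small where rates are low. Because the ranking of the two counts reverses when the drug also raises early AEs, neither view can stand in for the other. This is a cheap improvement that should be made, and the sections on the timing of the step must be reconciled before the cut-point is fixed.

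**What to change.** Keep the whole-trial endpoint. Add to SAP 8 and Table 3, overall and by SOC:

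- **(a) After the step.** Participants with at least one AE whose recorded onset date is on or after the dispensing at which the 160 mg step occurs, using the same scheduled visit in every arm. Compare 160 mg with placebo and 120 mg with placebo, with exact confidence intervals for active minus placebo. Show it both for those still under observation at the step and for all randomised, with numbers at risk. The first loses early leavers; the second counts them as free of late AEs and can hide harm.
- **(b) Before the step.** AEs with earlier onset, with the two active arms pooled (36 + 36 = 72) against placebo, since their doses are the same.

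Count a worsening only where it was entered as a new AE with its own onset date. The AE record lists severity, onset and resolution, but no dates of grade change.

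The cost is one more table from data already collected, with no change to conduct. The late comparison is supplementary and loses participants who left early, and the text should say so.

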Phase I Single Ascending Dose Study (SAD): A double-blind, placebo-controlled, ascending, single-dose safety, tolerability, and pharmacokinetic study of SRX246 in capsules was undertaken in healthy adult volunteers. A total of 49 Subjects were enrolled—37 males and 12 females with a mean age of 43.5 years. The Subjects were representative of different races: Caucasian (7), black/non-Hispanic (23), Hispanic (18), Asian/Pacific Islander (1). A single oral dose of SRX246 was administered to a total of 34 Subjects enrolled in a total of 7 separate cohorts. The dosing cohorts were as follows: 20 mg (5 Subjects), 80 mg (2 consecutive cohorts of 5 Subjects each), 160 mg (5 Subjects), 240 mg (5 Subjects), 320 mg (4 Subjects). There were a total of 15 placebo Subjects spread among all cohorts (2 per cohort except for Cohort 7 in which there were 3). All Subjects completed the study; there were no SAEs, deaths, or discontinuations.

Safety summary: A total of 25 adverse events (AEs) were recorded. Overall, no trend was identified in terms of specific organ system affected with increasing dose. In fact, the placebo Subjects experienced a higher absolute number of AEs than the experimental Subjects except for orthostatic tachycardia (OT), which is discussed below. In Cohort 1 (20 mg) a single AE (mild light headedness) was reported. There were no AEs reported in Cohort 2 (40 mg). In Cohort 3 (80 mg) elevations in heart rate (HR) immediately upon standing were described in 3 patients. At the time these events were observed, some of the HR readings were repeated manually; the elevation in HR could not be confirmed, and the “tachycardia” was not accompanied by any clinical symptoms. Nonetheless, the 80 mg dose was repeated in a new cohort of Subjects prior to dose escalation. In this new group of Subjects, there was no orthostatic tachycardia (OT) and no other AEs.

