With post-hoc review, a total of 10 additional OT AEs were documented within Cohorts 1, 2, 6 and 7, and were included in the study database. Upon unblinding the study, OT was the only AE noted where there was a higher overall incidence in the active Subjects than the placebo Subjects. However, no dose response relationship was observed as the dose of SRX246 increased from 20-320 mg. The OT AEs were not accompanied by BP changes, and no clinically significant EKG changes were identified during the study. Finally, no clinical signs/symptoms (e.g., chest pain, shortness of breath) were reported at the time the OT AEs were noted, and the Subjects did not experience any clinical sequelae.

PK Summary: The PK data demonstrate that SRX246 is orally bioavailable, with Mean Cmax and AUC values for plasma SRX246 concentration increasing in a dose-proportional manner as the SRX246 dose increased.

Overall conclusion: SRX246 is orally bioavailable as observed by dose-proportional increases in plasma levels, and is safe and well tolerated at the highest dose studied (320mg). Dose-limiting toxicity was not observed during the study. However, based on attaining adequate exposure levels at the highest dose, a determination was made to discontinue dose escalation and the study.

Phase I Multiple Ascending Dose Study (MAD): The results of the SAD study indicated that it would be safe to undertake a multiple ascending dose (MAD) study of SRX246 capsules in healthy volunteers. The SRX246 doses selected for use in the MAD study were 30, 60, and 120 mg administered q12h (i.e., 60, 120 and 240 mg total daily dose, respectively).

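### The final analysis compares preferred terms by arm only after an undefined organ-class difference, and no by-arm preferred-term table is planned otherwise

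*SAP*

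**What the plan says.** SAP section 8 first tests the overall proportion of participants with a treatment-emergent event. It then goes down one level: "this hypothesis will be repeated for assessing the percentage of study participants having at least one treatment-emergent AE within each MedDRA system organ class". The test is carried over from tolerability: "The same onesided CI will be used to test the same null hypothesis", with a margin of 0.5 and one-sided alpha of 0.025.

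Preferred terms come third, and only on a condition: "If there are specific differences within any specific SOC, then additional tests will compare differences across groups for specific MedDRA preferred terms". The stated purpose is "in order to further explore the cause of the observed differences". The step is thus a follow-up to an SOC finding and does not screen all terms.

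Nothing else in the planned output fills the gap. SAP Table 3 has overall rows only: any AE, treatment-related, serious, drug withdrawals, early terminations and deaths. SAP section 5 lists no adverse event table. Yet Protocol section 10.3 and SAP section 3 have every reported event recoded to MedDRA, so preferred-term data will exist for all participants.

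**The concern.** An SOC pools many unrelated terms. If one term is more frequent on drug but the class already contains many background events, the class-level difference is smaller relative to its noise than the term-level difference. A rule that looks at the term only when the class differs can then pass over the signal.

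The population makes this plausible. Protocol section 7 expects irritability, anger, aggression, depression and suicidality as part of the disease, so at least the classes holding behavioural terms may have substantial background in all three arms.

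The condition is also not operational. The SOC step is a non-inferiority test, whose output is whether a limit falls below 0.5. That is not a finding of a difference, so two analysts could apply the condition to the same data and reach opposite decisions about showing preferred terms.

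**Working it through.** **Arm size.** The plan states no figure for the SOC or preferred-term step. The only relevant planning figure is the arm size in Protocol section 8.2 and SAP section 9. With completer rates 0.80 and 0.60, margin 0.50, one-sided alpha 0.025 and 80% power:

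n = (1.960 + 0.842)² × (0.80×0.20 + 0.60×0.40) / (0.50 − 0.20)² = 7.849 × 0.40 / 0.09 = 34.88, so 35 per arm.

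The protocol calculation gives about 35 and the SAP about 36; n = 36 is used below.

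**Assumptions, because the documents give no term or SOC rates.** One dose is compared with placebo. The term has true rate 0% on placebo and 20% on drug. Other events in the same SOC occur at rate b in both arms, independently of the term. The SOC rate is then b on placebo and 1 − (1 − b)(0.80) on drug.

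**Direct comparison of the term.** With 0/36 on placebo, two-sided Fisher p is 0.054 for 5/36 on drug and 0.025 for 6/36. Six events are therefore needed, and P(X ≥ 6) for X binomial (36, 0.20) is 0.75.

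**Comparison of its SOC.** Exact enumeration of all 37 × 37 outcomes, under two readings of the undefined trigger:

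| Background b | SOC rate, placebo v drug | P(Fisher p<0.05, drug higher) | P(any numerical excess on drug) |
|---|---|---|---|
| 5% | 0.05 v 0.24 | 0.53 | 0.99 |
| 10% | 0.10 v 0.28 | 0.40 | 0.97 |
| 30% | 0.30 v 0.44 | 0.16 | 0.87 |
| 50% | 0.50 v 0.60 | 0.08 | 0.77 |

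On the Fisher reading, the loss against 0.75 is moderate in a rare class and severe in a common one. On the numerical-excess reading, the step usually opens.

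**The same thing in counts.** Take a term seen in 0/36 v 6/36 (p = 0.025). Backgrounds of 30%, 40% and 50% give about 11, 14 and 18 of 36 on placebo. The six drug participants add about 6 × (1 − b) new ones to the class: 4.2, 3.6 and 3.0.

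- 11 v 15: p = 0.46
- 14 v 18: p = 0.48
- 18 v 21: p = 0.64

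None is significant, and all are numerical excesses. Whether the preferred term is then compared depends wholly on which reading is applied.

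**Third reading: the SOC test as written.** Placebo minus drug for 18 v 21 is −0.083, with standard error √(0.50×0.50/36 + 0.583×0.417/36) = 0.117. The upper limit is −0.083 + 1.96 × 0.117 = 0.146 (Wald, standing in for the exact limit). This is below 0.5, so the null is rejected and nothing is flagged.

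**The case against.** **The trigger may be generous.** The SAP does not name Fisher's test or any p-value, and its wording about exploring observed differences can be read descriptively. On that reading all three count examples open the step. This stands, and it is why the conclusion cannot be that the step would stay shut.

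**Events are seen elsewhere.** A reader might infer that a masked term would never be looked at. The documents do not support that. The DSMB reviews partially unblinded data and monitors adverse event rates (Protocol section 9.8, SAP section 10.2). Aggregate reports of all events go to the medical monitor and DSMB (Protocol section 10.3.5), and the medical monitor reviews every serious event. Serious events and withdrawals due to adverse events appear by arm in Table 3 unconditionally. But the documents do not say that the DSMB sees preferred terms, the medical monitor's aggregate reports are blinded (SAP section 10.1), and neither review is the final analysis.

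**Some harms have their own measures.** The C-SSRS, orthostatic vital signs, EKG and AST/ALT are collected. This narrows the concern only in part: the SAP plans no post-baseline summary of them by arm, and suicidal ideation appears only as a baseline characteristic.

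**Phase I as proof.** A reader might take the single-dose study in Protocol section 2.2 as showing an organ-class look that hid orthostatic tachycardia. It does not. The organ-system statement there concerns trend with dose, and orthostatic tachycardia showed no dose response either; its excess was against placebo. No organ-class comparison of drug with placebo is reported, and ten of those events were added on post-hoc review, which is a matter of event capture.

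**Stepping down limits chance findings.** Going from class to term is a recognisable way to do that. It is a reason to keep formal tests few, but not to withhold a descriptive table. The SAP does not forbid such a table; it does not commit to one.

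**Conclusion.** The concern holds for the final analysis. By-arm preferred-term comparison depends on an SOC difference that is not defined, no by-arm preferred-term table is planned otherwise, and a specific signal in a common SOC can be missed.

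How often cannot be fixed from the documents. For a 0% v 20% term and backgrounds of 5% to 50%, the step opens with probability 0.53 down to 0.08 on a p<0.05 trigger, or 0.99 down to 0.77 on any numerical excess. These figures rest on assumed rates, independence within the class and 36 per arm. The finding that does not rest on them is that the trigger is missing.

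The direction and the 0.5 margin of the SOC test are a separate matter. Correcting both would not remove the dilution. The point has no bearing on the tolerability Go/No-Go decision or the sample size. It is a gap in safety reporting that is cheap to close.

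**What to change.** In SAP section 8, remove the condition on preferred terms. Add a table of every treatment-emergent preferred term within SOC by arm, showing the number and percentage of participants and, for each dose, the drug minus placebo difference with a two-sided 95% confidence interval. Produce it whatever the SOC results, and label it descriptive. Any formal preferred-term tests should stay exploratory; if a conditional test is kept, state the numerical rule that opens it. Pre-specified groupings of related terms across SOCs are optional.

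The cost is one paragraph and one standard table from data already coded to MedDRA. The downside is a longer table in which some differences will be chance, and the label should say so.
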